15.0 REPORTING OF UNANTICIPATED PROBLEMS, PROTOCOL DEVIATIONS AND ADVERSE EVENTS

The Principal Investigator is responsible for detecting, documenting, and reporting unanticipated problems, adverse events (AEs), including serious adverse events (SAEs), and deviations in accordance with NIH policy, IRB requirements, and federal regulations. Relatedness to the research of all serious adverse events will be determined by the PI in consultation with the Clinical Director (CD).

Serious unanticipated problems, serious adverse events (including deaths) that are not unanticipated problems and serious protocol deviations will be reported to the IRB and CD as soon as possible and in writing not more than 7 days after the PI first learns of the event, unless immediate reporting is waived for specific serious adverse events as noted below. Not serious unanticipated problems and not serious deviations will be reported to the IRB and CD as soon as possible and in writing not more than 14 days after the PI first learns of the event. Written reports will be submitted in PTMS.

All adverse events, deviations, and unanticipated problems will be summarized and reported at the time of Continuing Review.

The PI will immediately report SAEs to the Sponsor according to the requirements of 21 CFR 312.64(b). The PI will record non-serious AEs and report them to the Sponsor as soon as possible.

16.0 ALTERNATIVES TO PARTICIPATION

Current therapy for patients with RCD or ESCS and macular cystic changes is treatment with a topical or systemic CAI. This study calls for recruitment of patients that have not been exposed to CAI, have been unable to use CAI due to side effects, or have not had an adequate response to CAI.

17.0 PRIVACY

All research activities will be conducted in as private a setting as possible.

18.0 CONFIDENTIALITY

All medical records will be kept confidential and will only be reviewed by the participating investigators. Data will be kept in password-protected computers held at the NEI and The Emmes Corporation. Only study investigators and Emmes staff will have access to the study data. The participants' names will not appear on any of the data forms reported to the coordinating center. A unique identifier, a study registration number, will identify the participant to the coordinating center. Participants' personal information will be kept as private as possible. However, records can be inspected by organizations for quality assurance and data analysis.

These include the members of the IRB and the NEI SAE Review Committee. Clinical and demographic information will be kept in the Eye Clinic Electronic Medical Record (EMR). Access will be password-protected and restricted to authorized users. In most cases, the NIH will not release any information about research involvement without written permission. However, if the participant signs a release of information form, the NIH will give the requestor information from the participant's medical record. We will try to keep personal information as private as possible. However, medical records may be inspected by various governmental and regulatory entities for auditing and other purposes. De-identified results from this clinical trial will be posted on <http://www.clinicaltrials.gov>.

19.0 CONFLICT OF INTEREST

The NIH guidelines on conflict of interest were distributed to all the investigators and none of the NIH investigators had any conflicts of interest.

20.0 TECHNOLOGY TRANSFER

Horizon Pharma (formerly Vidara) will provide the investigational product (IFN gamma-1b injection solution, ACTIMMUNE®) as outlined in a signed clinical trial agreement with NEI (CTA #00935-13). NEI may provide summary information and de-identified coded data to Horizon Pharma, if requested. NEI will ship collected, coded samples to Horizon Pharma or their designee for IFN gamma level testing.

21.0 RESEARCH AND TRAVEL COMPENSATION

For this study, there is no compensation for participation. This protocol will include reimbursement for travel and subsistence.

APPENDIX 1: STUDY FLOWSHEET

Visit Schedule	Baseline	Day 1	Day 2	Day 3	Week 1	Week 2	Week 5	Week 6	Week 8	Week 52
Visit Number	000	000A	000B	000C	001	002	005	006	008	SFTY ⁸
Target Day from Baseline	0	1	2	3	7	14	35	42	56	365
Visit Window					±1 day	±5 days	±7 days	±7 days	±7 days	±30 days
Investigational Product										
Interferon Gamma-1b Dropperettes Dispensed		X ¹	X ¹	X ¹						
Drug Accountability Review						X				
General Assessments										
Medical/Ophthalmic History	X									
Brief Physical Examination	X									
Concomitant Medications Assessment	X	X	X	X		X	X		X	X
Adverse Event Assessment	X	X	X	X		X	X		X	X
Vital Signs	X	X	X			X			X	
Telephone Assessment					X			X		
Ophthalmic Assessments										
BCVA (EVA)	X	X	X	X		X	X		X	X
Manifest Refraction ²	X								X	
Slit Lamp Examination	X	X	X	X		X	X		X	X
Dilated Fundus Examination	X	X	X	X		X	X		X	X
Intraocular Pressure (IOP)	X	X	X	X		X	X		X	X
Color Vision Assessment (Cambridge Color Test)	X ³						X			
Color Fundus Photography (CFP)	X ³					X			X	
Fundus Autofluorescence (FAF)	X ³					X			X	
Lens Photography	X ³					X			X	
Optical Coherence Tomography (OCT)	X ⁴	X ⁴	X ⁴	X ⁴		X	X		X	
Fluorescein Angiogram (FA)	X ³					X				
Microperimetry	X ³		X				X		X	
Electroretinography (ERG)	X						X			
Electrooculography (EOG)	X		X			X	X		X	
NEI VFQ-25	X ³					X			X	
Research Sample Collection										
Skin Biopsy for iPSCs ⁵		X								
Blood Sample for iPSCs ⁵		X								

Visit Schedule	Baseline	Day 1	Day 2	Day 3	Week 1	Week 2	Week 5	Week 6	Week 8	Week 52
Visit Number	000	000A	000B	000C	001	002	005	006	008	SFTY ⁸
Laboratory Testing										
CBC with differential	X ³					X			X	
Chemistry Panels (Acute Care and Hepatic)	X ³					X			X	
Serum IFN gamma levels and antibody titers ⁶	X		X			X				
Pregnancy Testing ⁷	X						X		X	

- ¹ Investigational product may be instilled by clinic staff during the first three days of IP administration and will be prescribed as necessary to maintain the dosing regimen.
- ² BCVA with manifest refraction must be performed when scheduled and when there is a change in EVA of >10 E-ETDRS letters (> 0.20 logMAR) as compared with relevant baseline.
- ³ These procedures can be completed under NEI protocols 08-EI-0102 or 08-EI-0169 if performed within 9 days prior to Visit 000.
- ⁴ This test will be performed at least once but can be performed up to three times daily to assess for acute/subacute changes in macular cysts.
- ⁵ These procedures (skin biopsy for iPSCs and blood sample for iPSCs) may be performed at any study visit. The skin biopsy is only for participants who consent to providing skin biopsy samples for iPSC generation as this procedure is optional.
- ⁶ Collected samples will be shipped to Horizon Pharma (or their designee) for analysis.
- ⁷ This test is for women of childbearing potential only and they must have a negative test prior to the investigational product administration on enrollment day.
- ⁸ Visit records from a local ophthalmologist can substitute for the Week 52 safety visit if participant is unwilling or unable to come to NIH.

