4.4 Study Visits

Participants receiving IP will be provided with on-campus lodging for the first three days to complete the baseline assessments and for frequent monitoring to ensure good compliance and correct eye drop instillation technique (Days 1, 2 and 3). Scheduled clinic visits will occur at baseline, Days 1, 2 and 3, and Weeks 2, 5 and 8. A 52-week (one year) safety visit may be conducted at the NIH (on site) or with a local ophthalmologist (if the participant is unable/unwilling to come to NIH). Although there may be differences in testing among the various private physicians, at a minimum, all participants receiving IP must provide documentation of the assessments noted in Week 52 on the study flowsheet. After the participant signs a release of information with his/her ophthalmologist, the examination results will be sent to NEI. NEI will pay for the costs associated with obtaining medical records.

In addition, one of the investigators will conduct a phone interview with participants receiving IP at Weeks 1 and 6 to inquire about ocular complications. One or more unscheduled visits for safety assessment can be added based on the discretion of the investigators.

The regimen of IFN gamma-1b administration will consist of two weeks of therapy, dosing the study eye four times daily, with each dose consisting of a four-drop series, each drop spaced by 5 minutes, for a total of 16 drops delivered per day. The daily dose of IFN gamma-1b will be 112 µg topically (7 µg per drop, applied in 16 drops). Punctal occlusion will be employed to reduce systemic absorption. Investigators will train participants receiving IP on proper drop administration and monitor participants during the initial visits.

If at any time during the study participants experience ocular redness or other ocular concerns, they will be evaluated as soon as possible and the investigator may choose to terminate or reduce the dosage of the IFN gamma-1b eye drops. The dosage may be reduced to a three-drop series four times daily if symptomatic ocular surface disease and/or red eye develops.

Participants receiving IP may be restarted on the drops if the ocular condition resolves, at the investigator's and participant's discretion. Follow-up visits to manage ocular complications will be arranged, independent of and in addition to the prescribed visit schedule of the protocol.

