4.4.1 Study Evaluations

The following examinations will be performed at the study visits as indicated in the study flowsheet (Appendix 1). Examinations will be performed both as clinical care and for research purposes.

1. Medical/Ophthalmic History
2. Brief Physical Examination
3. Concomitant Medication Assessment
4. Adverse Event Assessment
5. Vital Signs (weight, blood pressure (BP), respiration, temperature)
6. Best-corrected Visual Acuity (BCVA) using EVA (Appendix 4)
7. Manifest Refraction
8. Slit Lamp Examination
9. Dilated Fundus Examination
10. Intraocular Pressure (IOP)
11. Color Vision Assessment (Cambridge Color Test)
12. Color Fundus Photography (CFP) / Fundus Autofluorescence Imaging (FAF)
13. Lens photography
14. Optical Coherence Tomography (OCT)
15. Fluorescein Angiography (FA)
16. Microperimetry
17. Electroretinography (ERG)
18. Electrooculography (EOG)
19. National Eye Institute Visual Functioning Questionnaire - 25 (VFQ – 25) (Appendix 3)
20. Serum Chemistry Panels (Acute Care and Hepatic)
21. Serum Chemistry to obtain IFN gamma levels and antibody titers
22. Complete Blood Count (CBC) with differential

23. Pregnancy Testing

24. Skin Biopsy and blood sample to derive iPSCs*

- a. A 3 mm skin biopsy may be collected. The same procedure will be used for adults and children. **Participants who do not agree to a skin biopsy will **not** be excluded.*
- b. Thirty (30) mL of blood may be collected by phlebotomy to derive iPSCs. For children, no more than the lesser of 5 mL/kg or 30 mL of blood will be collected.

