4.5.3 Preparation and Administration

Commercially-available Actimmune[®], manufactured by Horizon Pharma, will be used in this study and provided to the NIH CC Pharmacy. Vials of Actimmune[®] will be placed in a 2-8° C (36-46° F) refrigerator immediately upon receipt to ensure optimal retention of physical and biochemical integrity. The vials will not be frozen. Excessive or vigorous agitation will be avoided and the vials will not be shaken. The vials will be shipped from the NIH CC Pharmacy under controlled conditions to Pine Pharmaceuticals ([name]) to be re-packaged into single daily use 1 mL dropper bottles. IFN gamma-1b will be supplied to participants in the re-packaged single daily-use dropperettes to be stored in a 2-8° C (36-46° F) refrigerator. A single dropperette contains 1 mL of IFN gamma-1b (Actimmune[®]) at a

concentration of 200 µg/mL, which is equivalent to 28 drops. Each drop provides a dose of 7 µg of investigational product. Between daily uses, participants will store the open dropperette in the refrigerator or in a cooler with a cold pack at 2-8° C. Participants will be given cooler bags for transporting dropperettes. Once opened, each dropperette should be discarded within 24 hours. Participants will be given containers for disposal of the used dropperettes.

Participants will use a new dropperette each day as instructed from the Day 1 visit through the day prior to the Week 2 visit (see Appendix 2). Administration of topical IFN gamma-1b drops should be spaced throughout the day (approximately at breakfast, lunch, dinner and bedtime depending upon the dosage received) as instructed. Participants will be instructed to immediately discard dropperettes after each day's use in the provided disposal container which will be returned to the clinic at their next visit. Participants will be instructed on the proper administration techniques during their initial visit.

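### Serum IFN gamma and antibody sampling has one untimed on-drug level and no titre after Week 2, so a negative result would be weak evidence

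*Combined protocol and SAP*

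**What the plan says.** **Sampling.** In the Laboratory Testing block of Appendix 1, levels and titres share one row, "Serum IFN gamma levels and antibody titers", marked at Baseline, Day 2 and Week 2 and blank at every other visit. Section 4.4.1 lists them as a single item, "Serum Chemistry to obtain IFN gamma levels and antibody titers". Neither place states a draw time relative to a dose. CBC and chemistry panels are marked at Baseline, Week 2 and Week 8.

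**Dosing.** Section 4.4 gives 16 drops of 7 µg per day, 112 µg in all, as four series of four drops. Section 4.5.3 has participants use a new dropperette daily "as instructed from the Day 1 visit through the day prior to the Week 2 visit", with the series taken "approximately at breakfast, lunch, dinner and bedtime depending upon the dosage received". Footnote 1 of Appendix 1 adds: "Investigational product may be instilled by clinic staff during the first three days of IP administration".

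**Purpose and handling.** Section 4.4 treats systemic uptake as something to limit: "Punctal occlusion will be employed to reduce systemic absorption". Footnote 6 of Appendix 1 sends the samples to the manufacturer or its designee. Section 20.0 describes that shipment as being for level testing and does not mention titres. Sections 7.1, 7.2 and 8.1 name neither assay as an outcome and give no analysis for them.

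**The concern.** Safety and tolerability come first in the primary objective, and Section 2.0 includes systemic side effects. Minors from age 12 are eligible. The exclusion criteria name multiple sclerosis because IFN gamma may worsen it. The earlier human experience reported in Section 1.0 is five participants (2 + 2 + 1) given 10, 20 or 30 µg at a single session. This trial gives 112 µg daily, about 3.7 times the highest of those amounts (112 / 30), for roughly two weeks.

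This assay row is the only direct measure of systemic drug or of antibody formation in the flowsheet. If its timing lets real exposure or a real antibody response go unseen, a set of undetectable levels and negative titres says little, and a reader of the results could give it more weight than it can bear.

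**Working it through.** **Inputs.** Target days and windows come from Appendix 1: Week 2 is Day 14 ±5, Week 5 is Day 35 ±7 and Week 8 is Day 56 ±7. Dosing dates come from Section 4.5.3: first dose on Day 1, last dose on the day before the Week 2 visit. The dose comes from Section 4.4. The documents give no IFN gamma half-life, assay limit or antibody latency.

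**1. The plan's own figure.** 16 drops × 7 µg = 112 µg per day, which reproduces. The unrounded drop in Section 4.5.3 is 200 / 28 = 7.14 µg, giving 114.3 µg per day. The difference is rounding and does not matter here.

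**2. Where the levels fall.**
- Baseline precedes all dosing.
- Day 2 follows up to one full dosing day plus whatever has been given that morning: 112 + 28k µg, where k is the number of Day 2 series already given (0 to 4) and 28 = 4 × 7. If k = 0, the last drop was at bedtime the night before.
- Week 2 at its target date follows 13 dosing days: 13 × 112 = 1,456 µg. Across the window it follows 8 to 18 dosing days: 896 to 2,016 µg. The last drop was on the previous day.

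Of the two post-baseline levels, one is on drug and neither has a stated time after a dose.

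**3. What an overnight gap could cost (assumptions).** Take 8 to 14 h since the bedtime series, simple first-order decay, and a half-life h from 1 to 12 h. The fraction remaining is 0.5^(t/h):

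| Half-life | t = 8 h | t = 14 h |
|---|---|---|
| 1 h | 0.4% | 0.006% |
| 2 h | 6% | 0.8% |
| 4 h | 25% | 9% |
| 6 h | 40% | 20% |
| 12 h | 63% | 45% |

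The table applies to the Week 2 draw, and equally to a Day 2 draw taken before that day's first series. The range is too wide to say that Week 2 would miss exposure. It does show that a level cannot be interpreted without the time since the last drop.

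**4. Where the titres fall, in days after first dose (visit day minus 1).**

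| Visit | Target | Window | Titre planned |
|---|---|---|---|
| Day 2 | 1 | none stated | yes |
| Week 2 | 13 | 8 to 18 | yes |
| Week 5 | 34 | 27 to 41 | no |
| Week 8 | 55 | 48 to 62 | no |

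One of the three titres is close to a repeat of baseline. A response that first appears after the Week 2 visit is not observed. Week 8 falls 43 days after the last dose at target dates (56 − 13).

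**5. Course length.** Section 4.4 describes two weeks of therapy. Read as 14 days, that is 14 × 112 = 1,568 µg. Section 4.5.3 with the flowsheet's target dates implies 13 dosing days and 1,456 µg. The passages must be reconciled.

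**The case against.** A reader might infer that this schedule cannot detect either absorption or antibody, or that negative results are to be expected whatever the truth. The documents do not support that. Day 2 is drawn during treatment and can show systemic drug. With a longer half-life, so can Week 2. The Baseline and Week 2 titres together can show an early antibody response. The stronger claim would need a half-life, an assay limit and an antibody latency, none of which is given.

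Other points on the plan's side also have force:
- Neither assay is a named outcome, and no planned conclusion rests on them.
- Systemic safety is also followed through adverse events at every clinic visit, vital signs, and CBC and chemistry through Week 8. Section 1.0 reports no systemic adverse events in the earlier study, though at lower, short-term doses.
- With so few participants, even well-timed negatives would be limited. Zero positives in 10 leaves a one-sided 95% upper bound of 1 − 0.05^(1/10) = 26%; in 5 it is 45%.
- Section 4.4 allows drops to be reduced, interrupted or restarted, so the interval between last drop and Week 2 will not be the same for everyone.
- Appendix 2 and part of Section 5 were not in the text available here. Nothing above relies on their silence, and draw-time instructions could stand there.

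These points limit the claim and its severity. They do not explain a titre one day after first exposure, or the lack of one at Week 8 when blood is already being taken.

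**Conclusion.** The point holds in limited form. Followed exactly, the schedule gives one on-drug level with no stated time after a dose, none late in the course, a Day 2 titre that adds little to baseline, and no titre later than 8 to 18 days after first dose. Peak or late-course exposure and later antibody responses may be missed. A negative result would be weak evidence that the drug is not absorbed or not immunogenic.

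Confidence is high on the sampling and dosing dates, which come straight from Appendix 1 and Section 4.5.3. It is moderate on how much is missed, because half-life, the overnight interval and antibody latency are assumptions. The antibody part is the firmer of the two, since it needs only the possibility of a response appearing after Week 2. The sponsor should act because the change is small. The primary and secondary outcomes are not affected.

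**What to change.** In Appendix 1, split the combined row and:

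1. Move the Day 2 antibody titre to Week 8, using the blood already drawn there for CBC and chemistry. Titres would then be at Baseline, Week 2 and Week 8.
2. Keep the Day 2 IFN gamma level, but draw it at a fixed, recorded interval after a clinic-observed instillation. Footnote 1 already allows staff to instil the drops, and participants are lodged on campus.
3. Record the time since the last drop for every level, and report the Week 2 level as post-treatment.

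Separately, reconcile the course length in Section 4.4 with the dosing dates in Section 4.5.3 and the flowsheet.

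**Cost.** A flowsheet amendment, with three levels and three titres as now and no extra visit or venepuncture. The Day 2 draw must wait for its set time, and one sample ships later. The sponsor must confirm that the shipping arrangement in Section 20.0, which names only level testing, covers titres. The change does not add an on-drug level late in the course, so that gap remains and should be acknowledged when the results are reported.

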APPENDIX 3: NATIONAL EYE INSTITUTE VISUAL FUNCTIONING QUESTIONNAIRE-25**©1996, Rand**

Instructions:

I'm going to read you some statements about problems which involve your vision or feelings that you have about your vision condition. After each question I will read you a list of possible answers. Please choose the response that best describes your situation.

Please answer all the questions as if you were wearing your glasses or contact lenses (if any).

Please take as much time as you need to answer each question. All your answers are confidential. In order for this survey to improve our knowledge about vision problems and how they affect your quality of life, your answers must be as accurate as possible. Remember, if you wear glasses or contact lenses for a particular activity, please answer all of the following questions as though you were wearing them.

PART 1 - GENERAL HEALTH AND VISION

1. In general, would you say your overall health is*:

READ CATEGORIES:

(Circle One)

Excellent	1
Very Good.....	2
Good.....	3
Fair	4
Poor	5

2. At the present time, would you say your eyesight using both eyes (with glasses or contact lenses, if you wear them) is excellent, good, fair, poor, or very poor or are you completely blind?

READ CATEGORIES:

(Circle One)

Excellent	1
Good.....	2
Fair	3
Poor	4
Very Poor	5
Completely Blind	6

3. How much of the time do you worry about your eyesight?

READ CATEGORIES:

(Circle One)

None of the time..... 1
A little of the time..... 2
Some of the time..... 3
Most of the time..... 4
All of the time..... 5

4. How much pain or discomfort have you had in and around your eyes (for example, burning, itching, or aching)? Would you say it is:

READ CATEGORIES:

(Circle One)

None..... 1
Mild..... 2
Moderate..... 3
Severe..... 4
Very severe..... 5

PART 2 - DIFFICULTY WITH ACTIVITIES

The next questions are about how much difficulty, if any, you have doing certain activities wearing your glasses or contact lenses if you use them for that activity.

5. How much difficulty do you have reading ordinary print in newspapers? Would you say you have:

(READ CATEGORIES AS NEEDED)

(Circle One)

No difficulty at all..... 1
A little difficulty..... 2
Moderate difficulty..... 3
Extreme difficulty..... 4
Stopped doing this because of your eyesight..... 5
Stopped doing this for other reasons or not
interested in doing this..... 6

6. How much difficulty do you have doing work or hobbies that require you to see well up close, such as cooking, sewing, fixing things around the house, or using hand tools? Would you say:

(READ CATEGORIES AS NEEDED)

(Circle One)

No difficulty at all 1
A little difficulty 2
Moderate difficulty 3
Extreme difficulty 4
Stopped doing this because of your eyesight 5
Stopped doing this for other reasons or not
interested in doing this 6

7. Because of your eyesight, how much difficulty do you have finding something on a crowded shelf?

(READ CATEGORIES AS NEEDED)

(Circle One)

No difficulty at all 1
A little difficulty 2
Moderate difficulty 3
Extreme difficulty 4
Stopped doing this because of your eyesight 5
Stopped doing this for other reasons or not
interested in doing this 6

8. How much difficulty do you have reading street signs or the names of stores?

(READ CATEGORIES AS NEEDED)

(Circle One)

No difficulty at all 1
A little difficulty 2
Moderate difficult 3
Extreme difficulty 4
Stopped doing this because of your eyesight 5
Stopped doing this for other reasons or not
interested in doing this 6

9. Because of your eyesight, how much difficulty do you have going down steps, stairs, or curbs in dim light or at night?

(READ CATEGORIES AS NEEDED)

(Circle One)

No difficulty at all 1
A little difficulty 2
Moderate difficulty 3
Extreme difficulty 4
Stopped doing this because of your eyesight 5
Stopped doing this for other reasons or not
interested in doing this 6

10. Because of your eyesight, how much difficulty do you have noticing objects off to the side while you are walking along?

(READ CATEGORIES AS NEEDED)

(Circle One)

No difficulty at all 1
A little difficulty 2
Moderate difficulty 3
Extreme difficulty 4
Stopped doing this because of your eyesight 5
Stopped doing this for other reasons or not
interested in doing this 6

11. Because of your eyesight, how much difficulty do you have seeing how people react to things you say?

(READ CATEGORIES AS NEEDED)

(Circle One)

No difficulty at all 1
A little difficulty 2
Moderate difficulty 3
Extreme difficulty 4
Stopped doing this because of your eyesight 5
Stopped doing this for other reasons or not
interested in doing this 6

12. Because of your eyesight, how much difficulty do you have picking out and matching your own clothes?

(READ CATEGORIES AS NEEDED)

(Circle One)

No difficulty at all 1
A little difficulty 2
Moderate difficulty 3
Extreme difficulty 4
Stopped doing this because of your eyesight 5
Stopped doing this for other reasons or not
interested in doing this 6

13. Because of your eyesight, how much difficulty do you have visiting with people in their homes, at parties, or in restaurants ?

(READ CATEGORIES AS NEEDED)

(Circle One)

No difficulty at all 1
A little difficulty 2
Moderate difficulty 3
Extreme difficulty 4
Stopped doing this because of your eyesight 5
Stopped doing this for other reasons or not
interested in doing this 6

14. Because of your eyesight, how much difficulty do you have going out to see movies, plays, or sports events?

(READ CATEGORIES AS NEEDED)

(Circle One)

No difficulty at all 1
A little difficulty 2
Moderate difficulty 3
Extreme difficulty 4
Stopped doing this because of your eyesight 5
Stopped doing this for other reasons or not
interested in doing this 6

15. Now, I'd like to ask about driving a car. Are you currently driving, at least once in a while?

(Circle One)

Yes 1

Skip To Q 15c

No..... 2

15a. IF NO, ASK: Have you never driven a car or have you given up driving?

(Circle One)

Never drove..... 1

Skip To Part 3, Q 17

Gave up 2

15b. IF GAVE UP DRIVING: Was that mainly because of your eyesight, mainly for some other reason, or because of both your eyesight and other reasons?

(Circle One)

Mainly eyesight..... 1

Skip To Part 3, Q 17

Mainly other reasons..... 2

Skip To Part 3, Q 17

Both eyesight and other reasons 3

Skip To Part 3, Q 17

15c. IF CURRENTLY DRIVING: How much difficulty do you have driving during the daytime in familiar places? Would you say you have:

(Circle One)

No difficulty at all 1

A little difficulty 2

Moderate difficulty 3

Extreme difficulty 4

16. How much difficulty do you have driving at night? Would you say you have:

(READ CATEGORIES AS NEEDED)

(Circle One)

No difficulty at all 1

A little difficulty 2

Moderate difficulty 3

Extreme difficulty 4

Stopped doing this because of your eyesight..... 5

Stopped doing this for other reasons or not
interested in doing this 6

16a. How much difficulty do you have driving in difficult conditions, such as in bad weather, during rush hour, on the freeway, or in city traffic? Would you say you have:

(READ CATEGORIES AS NEEDED)

(Circle One)

- No difficulty at all 1
- A little difficulty 2
- Moderate difficulty 3
- Extreme difficulty 4
- Stopped doing this because of your eyesight 5
- Stopped doing this for other reasons or not
interested in doing this 6

PART 3: RESPONSES TO VISION PROBLEMS

The next questions are about how things you do may be affected by your vision. For each one, I'd like you to tell me if this is true for you all, most, some, a little, or none of the time.

(Circle One On Each Line)

READ CATEGORIES:	All of the time	Most of the time	Some of the time	A little of the time	None of the time
17. Do you accomplish less than you would like because of your vision?	1	2	3	4	5
18. Are you limited in how long you can work or do other activities because of your vision?	1	2	3	4	5
19. How much does pain or discomfort in or around your eyes , for example, burning, itching or aching, keep you from doing what you'd like to be doing? Would you say:	1	2	3	4	5

For each of the following statements, please tell me if it is definitely true, mostly true, mostly false or definitely false for you or you are not sure.

(Circle One On Each Line)

READ CATEGORIES:	Definitely true	Mostly true	Not sure	Mostly false	Definitely false
20. I stay home most of the time because of my eyesight.	1	2	3	4	5
21. I feel frustrated a lot of the time because of my eyesight.	1	2	3	4	5
22. I have much less control over what I do, because of my eyesight.	1	2	3	4	5
23. Because of my eyesight, I rely too much on what other people tell me .	1	2	3	4	5
24. I need a lot of help from others because of my eyesight.	1	2	3	4	5
25. I worry about doing things that will embarrass myself or others , because of my eyesight.	1	2	3	4	5

That's the end of the interview. Thank you very much for your time and your help.

